	
length of the surgery. It is possible that the bolus or continuous infusion may be ongoing at the start of surgery. There are 2 possible dosing regimens as described below:
 

 
Extended Infusion
 
Following the primary andexanet bolus and infusion (~2.5 hours), the andexanet infusion will be continued at the low dose of andexanet (4 mg/min) if the surgery and immediate post-operative period extend longer than the primary bolus and infusion. The extended infusion will continue through the end of the surgery and the immediate post-operative period, not to exceed 6 hours total.
 
Criteria for Re-Dosing with Andexanet
 
Consider re-dosing with andexanet (low-dose bolus + infusion) only if:
 
 a) New, clinically significant, surgery-related post-operative bleeding occurs after initial course of andexanet (primary bolus + infusion and extended dosing, as applicable) is completed, AND b) The treating physician has clinical suspicion that the patient still has levels of FXa inhibition sufficient to contribute to the bleeding, AND c) Re-dosing initiation occurs within 12 hours after the start of the first course of andexanet treatment. 	
lasting at least 120 minutes, irrespective of the length of the surgery. It is possible that the bolus or The continuous infusion may must be ongoing at the start of surgery, and must continue until the end of surgery even if extended treatment is required. There are 2 possible dosing regimens as described below:
 

 
*Extended Infusion (Additional low-dose 4 mg/min infusion up to 4 hours)
 
Following the primary andexanet bolus and 120-minute infusion (~2.5 hours), the andexanet infusion will be continued at the low dose of andexanet (4 mg/min) if the surgery and immediate post-operative period extends longer than the primary bolus and infusion. The extended infusion will (1) must continue at least through the end of the surgery and (2) may additionally continue during the immediate post-operative period, (per investigator discretion), and (3) should not exceed 6 hours.
 
The total duration of dosing including initial bolus, 120-minute infusion, and any extended infusion, should not exceed 6.5 hours. The limit of planned duration of infusion is stipulated to balance declining anti-fXa plasma levels and acceptable exposure to andexanet.
 
Criteria for Re-Dosing with Andexanet
 
Consider re-dosing with andexanet (low-dose bolus + 120 min infusion) only if:
 
 a) New, clinically significant, surgery-related post-operative bleeding occurs after initial course of andexanet (primary bolus + infusion and extended dosing, as applicable) is completed, AND b) The treating physician has clinical 	

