3.4.2 Rationale for the Dose Regimen	
 Low dose: 400 mg IV bolus at a rate of 30 mg/min (duration of approximately 15 minutes) followed by a continuous infusion at a target rate of 4 mg/min for 120 minutes irrespective of the duration of surgery (extended infusion at the discretion of the Investigator). High dose: 800 mg IV bolus at a rate of 30 mg/min (up to 30 minutes) followed by a continuous infusion at a target rate of 8 mg/min for 120 minutes irrespective of the duration of surgery (extended infusion at the discretion of the Investigator). 
Data from the Phase 3 studies with apixaban and rivaroxaban, as well as a recently completed Phase 1 study of Generation 2 andexanet in healthy volunteers (Study 16-512-Direct Inhibitors; Section 1.4.3), confirm the levels of FXa inhibition and recovery of TG observed in the Phase 2 study.
	
 Low dose: 400 mg IV bolus at a rate of 30 mg/min (duration of approximately 15 minutes) followed by a continuous infusion at a target rate of 4 mg/min for 120 minutes irrespective of the duration of surgery (extended infusion at the discretion of the Investigator). High dose: 800 mg IV bolus at a rate of 30 mg/min (up to duration of approximately 30 minutes) followed by a continuous infusion at a target rate of 8 mg/min for 120 minutes irrespective of the duration of surgery (extended infusion at the discretion of the Investigator). 
Extended infusion at the low-dose (4 mg/min) may be administered for up to an additional 4 hours after initial dosing (bolus + infusion) is completed (1) in order to ensure mandatory continuous infusion from start to end of surgery, and (2) may continue into the immediate post-operative coverage per investigator discretion. Total dosing time (initial bolus + 120 minute infusion + any extended infusion) should be less than 6.5 hours.
 
Evidence to support this dosing regimen comes from PK/PD modeling that included results from the ANNEXA-4 study in bleeding patients. Data from the Phase 3 studies with apixaban and rivaroxaban, as well as a recently completed Phase 1 study of Generation 2 andexanet in healthy volunteers (Study 16-512-Direct Inhibitors; Section 1.4.3), confirm the levels of FXa inhibition and recovery of TG observed in the Phase 2
	Included more details about dosing.	NS

		study.		

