	
duration of surgery. The start of the bolus will occur prior to, but not more than 30 minutes before, the start of surgery (i.e., at the first incision). It is possible that the bolus or infusion may be ongoing at the start of surgery. There are 2 possible dosing regimens (Table 2).
 
If the initial andexanet dosing regimen (bolus plus continuous infusion; ~2.5 hours) is completed prior to the end of the procedure, the infusion should continue at a low dose (4 mg/min) through the end of the surgery and the immediate post-operative period. To facilitate the extended infusion, approximately 30 minutes prior to the end of the andexanet infusion, the investigator should inform the pharmacy whether additional andexanet will be needed, to allow time for preparation. The total length of the initial course of andexanet (initial bolus/infusion plus extended infusion) should last no longer than 6 hours.
 
If a post-operative patient meets the applicable criteria for andexanet re-dosing (Table 2), he/she may be re-dosed. All patients that are re-dosed will be administered a low-dose bolus (400 mg) plus continuous infusion (4 mg/min for 120 minutes). If a patient is re-dosed, a baseline anti-fXa activity sample will be drawn beforehand; no post-initiation anti-fXa activity will be obtained.
	
<Figure 3 inserted>
 
Key Dosing Directives:
 
 Initial Bolus (low/high-dose) must be completed prior to start of surgery (initial skin incision) Initial dosing (low/high-dose bolus + 120-min infusion) should be completely administered irrespective of surgery length. Infusion should continue throughout the duration of surgery, defined as skin incision to skin closure. Extended infusion (up to 4 hours at 4 mg/min) (1) may be administered to ensure continuous infusion to match the duration of the surgery, and (2) can additionally proceed into the immediate postoperative period per investigator discretion. 
Initial Dosing (Bolus + 2-hour infusion):
 
The initial andexanet dosing regimen will consist of the following:
 
 1. an IV bolus, (to be completed prior to surgery) 
followed immediately followed by
 
 2. an IV continuous infusion lasting for at least 2 hours, (irrespective of the duration of surgery). 
The start of the bolus will occur prior to, but should be initiated not more than 30 minutes before, and must be completed by, the start of surgery (i.e., at the first incision). The bolus will be followed immediately by a continuous infusion lasting at least 120 minutes, irrespective of the length of the surgery. It is possible that the bolus or infusion may be
	
andexanet dosing rules in relation to surgery timing and procedures.
	

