		
bolus/infusion plus extended infusion) should last no longer than 6 hours.
 
Allowable Total Length of Dosing (Initial + Extended = up to 6.5 hours):
 
The total length of the initial dosing duration of andexanet (initial infusion plus extended infusion) should last no longer than 6.5 hours. Total study drug administration greater than 6.5 hours, while not prohibited, is strongly discouraged.
 
Re-dosing:
 
If a post-operative patient meets the applicable criteria for andexanet re-dosing (Table 2), he/she may be re-dosed. All patients that are re-dosed will be administered a low-dose bolus (400 mg) plus continuous infusion (4 mg/min for 120 minutes). If a patient is re-dosed, a baseline anti-fXa activity sample will be drawn beforehand for central laboratory analysis; no post-initiation anti-fXa activity will be obtained analyzed via local laboratory.
		
7.2.2 Blood Products	Use of procoagulant factor infusions (e.g., 3 or 4-factor PCC/activated PCC, rfVIIa, plasma, FFP) and whole blood intraoperatively or within 12 hours following surgery will result in the patient being considered having poor hemostatic efficacy (see Table 3) with andexanet.	Use of procoagulant factor infusions (e.g., 3 or 4-factor PCC/activated PCC, rfVIIa, plasma, FFP) and whole blood intraoperatively or within 12 hours following surgery will result in the patient being considered having poor hemostatic efficacy (see Table 3) with andexanet.	Removed text to clarify the criteria for poor hemostatic efficacy.	NS

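### The Amendment 1 dosing text disagrees on whether infusion to the end of surgery is required, and on what the 6.5-hour limit covers and how firm it is

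*Protocol*

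**What the plan says.** The clean Amendment 1 text of the synopsis and Sections 1 to 8 is not among the material shown. The amended dosing rules are therefore visible only in the new-text column of Protocol Appendix G. All the statements below come from that column, so this is not a comparison of old text with new.

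**Obligation**
- Synopsis, Test Product row: the infusion "must continue until the end of surgery even if extended treatment is required".
- Section 3.4.2 row: the extension exists to secure an infusion described as mandatory from start to end of surgery.
- Section 6.2 row: "Extended infusion (up to 4 hours at 4 mg/min) (1) may be administered to ensure continuous infusion to match the duration of the surgery". Elsewhere in the same row, the infusion *should* go on at 4 mg/min at least to skin closure if the initial regimen ends first.
- Synopsis Study Design row and Section 3.1 row: the infusion *should* run to the end of surgery, but additional andexanet, with extension named, *may* be given at the investigator's discretion when criteria are met.

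**Total limit**
- Synopsis, Test Product row: bolus, 120-minute infusion and extension together should not go beyond 6.5 hours.
- Section 3.4.2 row: "Total dosing time (initial bolus + 120 minute infusion + any extended infusion) should be less than 6.5 hours".
- Section 6.2 row: "andexanet (initial infusion plus extended infusion) should last no longer than 6.5 hours", followed by "Total study drug administration greater than 6.5 hours, while not prohibited, is strongly discouraged".

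**Length of the extension**
- Synopsis heading: "Extended Infusion (Additional low-dose 4 mg/min infusion up to 4 hours". The Section 3.4.2 and 6.2 rows and the revised dosing table also give 4 hours.
- The synopsis paragraph under that heading, whose subject is the extended infusion: "per investigator discretion), and (3) should not exceed 6 hours".

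**The concern.** Andexanet exposure during the operation is the intervention under study, and Section 11.5.1 scores hemostasis from the start of surgery to the end of the procedure. For any operation that outlasts the 2-hour initial infusion, one site can read the extension as required and another as optional, each with text to support it. Section 11.9 plans subgroups for operations of 2 to 4 hours and over 4 hours, so the protocol itself provides for such operations.

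Three things are at stake.
- The hemostasis and thrombotic-event rates in longer operations would mix two regimens.
- The secondary endpoint depends on when the infusion ends. Sections 11.5.1 and 11.5.2.2 close the anti-fXa evaluation period just before the end of the infusion. Appendix A, footnote 2, asks for the end-of-surgery sample before the infusion is stopped, which presumes drug is still running at closure.
- A monitor cannot classify either an omitted extension or an overrun of the limit as a deviation.

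**Working it through.** **Inputs** (Appendix G, Section 3.4.2 row): bolus 400 mg or 800 mg at 30 mg/min; initial infusion 4 or 8 mg/min for 120 minutes; extension 4 mg/min. Initial course:
- Low dose: 400 + 4 × 120 = 880 mg, lasting 400/30 + 120 = 133.3 min = 2.22 h.
- High dose: 800 + 8 × 120 = 1,760 mg, lasting 800/30 + 120 = 146.7 min = 2.44 h.

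**1. The plan's own total.** The nominal initial course of about 2.5 h plus a 4 h extension is 6.5 h, which reproduces the stated limit. At the stated bolus rate, the total is 2.22 + 4 = 6.22 h (low) or 2.44 + 4 = 6.44 h (high). A 4 h extension and a 6.5 h limit with the bolus counted therefore fit together.

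**2. Required versus discretionary extension.** The bolus must be finished before incision and the infusion follows at once, so the initial infusion ends about 2 h into surgery. The exclusion criteria bar only operations predicted to last over 4 h. A 4-hour operation is thus eligible and outlasts the initial infusion by about 2 h. Extension dose: 4 × 120 = 480 mg.
- Low dose: 880 + 480 = 1,360 mg against 880 mg (480/880 = +55%).
- High dose: 1,760 + 480 = 2,240 mg against 1,760 mg (480/1,760 = +27%).

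**3. Bolus counted or not.** Extension left within 6.5 h:
- Bolus counted: 6.5 − 2.22 = 4.28 h (low) or 6.5 − 2.44 = 4.06 h (high).
- Bolus not counted: 6.5 − 2 = 4.5 h.

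The most that 4.5 h could add to 4 h is 4 × 30 = 120 mg. Against a course with a 4 h extension (880 + 960 = 1,840 mg; 1,760 + 960 = 2,720 mg) that is 6.5% or 4.4%.

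**4. The 6-hour sentence, if it is live.**
- Extension dose: 4 × 360 = 1,440 mg against 4 × 240 = 960 mg.
- Course total: 2,320 mg against 1,840 mg (low, +26%) or 3,200 mg against 2,720 mg (high, +18%).
- Duration: 2.22 + 6 = 8.22 h or 2.44 + 6 = 8.44 h, about 2 h beyond the limit in the next paragraph.

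**5. Secondary endpoint.** Appendix A schedules post-bolus anti-fXa samples after the bolus, shortly before the end of the initial infusion, and at the end of surgery. In an operation longer than the initial infusion, the third sample falls inside the evaluation period only if the infusion was extended. The nadir is then the lowest of up to three values rather than two, and an added value can lower it but not raise it.

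**The case against.** The case on the other side is substantial, and much of it stands.

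- **The source is a tracked-change table.** Strikethrough was lost when the PDF was read, and deleted words run into added ones; the sentence with the 6-hour figure shows this. The superseded text had a 6-hour total, so the figure may be a remnant. It may also be live, because the sentence has no other number to complete it. The material shown cannot settle this.
- **A reader might infer three competing maxima of 4, 4.5 and 6 hours.** The documents do not support that. The 4.5 hours is stated nowhere and arises only because one sentence omits the bolus. Section 6.2 itself sets a maximum of 4 additional hours and defines initial dosing as bolus plus infusion.
- **A reader might infer that even a 4-hour extension breaks the requirement to stay under 6.5 hours.** That needs the bolus rounded to 30 minutes; at the stated rate the high-dose total is 6.44 h.
- **A reader might infer that infusing to the end of surgery and respecting the limit cannot both be followed.** Section 6.2 partly answers this by allowing the total to be exceeded, though it discourages it. The case is also narrow: 2 h of initial infusion plus 4 h of extension cover about 6 h from the end of the bolus, so surgery would have to run about 2 h past the 4 h eligibility limit.
- **Most of the obligation text can be read as one scheme**, with cover to skin closure and discretion afterwards. This removes part of the conflict. It does not remove the discretion sentences in the Study Design and Section 3.1 rows, which carry no such limit, nor the optional wording in Section 6.2 about matching the duration of surgery.
- **Extensions must be justified in the eCRF**, so exposure can be traced. That shows what was given, not whether it complied.

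**Conclusion.** The inconsistency is real, but it lies mainly in obligation and in the scope and status of the total limit. Infusion to the end of surgery is variously required, recommended, permitted and discretionary. The 6.5-hour limit includes the bolus in some places and does not name it in another, and it ranges from a ceiling to guidance.

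The exposure difference that matters comes from required versus discretionary extension: 480 mg, or 55% (low dose) and 27% (high dose) of the initial course, for an operation ending 2 h after the initial infusion. This assumes that one site extends to closure and another does not extend at all. The documents do not say how many patients would be affected. Whether the bolus counts is worth at most 120 mg (4% to 7% of the course), and the 4-hour maximum in Section 6.2 blocks even that.

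The 6-hour sentence remains conditional on the clean Amendment 1 text. If it is live, it is a further contradiction of 480 mg and about 2 h. If it is a remnant, that part falls away and the rest stands.

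**What to change.** Check the 6-hour sentence against the clean Amendment 1 synopsis. Then reconcile the synopsis (Study Design, Test Product and Maximum Length of Dosing), Sections 3.1, 3.4.2 and 6.2, and the revised dosing table, so that they agree on:

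- whether extension to skin closure is required or discretionary, kept separate from post-operative continuation;
- the maximum length of the extension;
- whether the bolus counts toward the total limit;
- whether that limit is firm or guidance;
- how the instruction to continue and the limit apply together when surgery outlasts the limit, and what is recorded as a deviation.

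The sponsor decides which values and rules stand. The cost is protocol wording and a clarification to sites and pharmacies, with no added procedures or patients.

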3.4.2 Rationale for the Dose Regimen	
 Low dose: 400 mg IV bolus at a rate of 30 mg/min (duration of approximately 15 minutes) followed by a continuous infusion at a target rate of 4 mg/min for 120 minutes irrespective of the duration of surgery (extended infusion at the discretion of the Investigator). High dose: 800 mg IV bolus at a rate of 30 mg/min (up to 30 minutes) followed by a continuous infusion at a target rate of 8 mg/min for 120 minutes irrespective of the duration of surgery (extended infusion at the discretion of the Investigator). 
Data from the Phase 3 studies with apixaban and rivaroxaban, as well as a recently completed Phase 1 study of Generation 2 andexanet in healthy volunteers (Study 16-512-Direct Inhibitors; Section 1.4.3), confirm the levels of FXa inhibition and recovery of TG observed in the Phase 2 study.
	
 Low dose: 400 mg IV bolus at a rate of 30 mg/min (duration of approximately 15 minutes) followed by a continuous infusion at a target rate of 4 mg/min for 120 minutes irrespective of the duration of surgery (extended infusion at the discretion of the Investigator). High dose: 800 mg IV bolus at a rate of 30 mg/min (up to duration of approximately 30 minutes) followed by a continuous infusion at a target rate of 8 mg/min for 120 minutes irrespective of the duration of surgery (extended infusion at the discretion of the Investigator). 
Extended infusion at the low-dose (4 mg/min) may be administered for up to an additional 4 hours after initial dosing (bolus + infusion) is completed (1) in order to ensure mandatory continuous infusion from start to end of surgery, and (2) may continue into the immediate post-operative coverage per investigator discretion. Total dosing time (initial bolus + 120 minute infusion + any extended infusion) should be less than 6.5 hours.
 
Evidence to support this dosing regimen comes from PK/PD modeling that included results from the ANNEXA-4 study in bleeding patients. Data from the Phase 3 studies with apixaban and rivaroxaban, as well as a recently completed Phase 1 study of Generation 2 andexanet in healthy volunteers (Study 16-512-Direct Inhibitors; Section 1.4.3), confirm the levels of FXa inhibition and recovery of TG observed in the Phase 2
	Included more details about dosing.	NS

		study.		
3.4.3 Rationale for Extended Infusion or Re-Dosing of Andexanet	
N/A
 
...
 
Investigators will be required to document in the case report form (CRF) the clinical justification for why subjects require extended infusion of andexanet or additional dosing of andexanet during surgery.
	
Re-dosing Criteria:
 
Factors that may determine if re-dosing is appropriate include the treating surgeon's consideration of patient factors, such as degree of visible bleeding, hemodynamic stability, need for hemostatic support products, or to avoid reoperation to control bleeding. The Investigator may also consider clinical suspicion that the patient has levels of FXa inhibition sufficient to contribute to bleeding based on patient factors such as time from last FXa inhibitor dose, safety assessments required by the protocol or routine care and renal function. Additionally, the need for re-operation to control bleeding may be considered reason re-dose to avoid the additional procedure.
 
...
 
Investigators will be required to document in the electronic case report form (eCRF) the clinical justification for why subjects require extended infusion of andexanet or additional dosing of andexanet during surgery.
	Added a small section to define criteria for re-dosing.	S
3.5 Safety Plan and Monitoring	
To mitigate the risk of TEs, Investigators are encouraged to consider resumption of an anti-thrombotic agent as soon as it is clinically appropriate.
 
...
 
Whether or not patients have been discharged from the hospital, they will undergo the Study Day 3, and Follow-up Day 30 visits to assess safety
	
To mitigate the risk of TEs, Investigators are encouraged to consider resumption of an anti-thrombotic agent (preferably oral) as soon as it is clinically appropriate. Additional clinical precautions to mitigate thrombotic risk in postoperative care such as early mobilization, sequential compression devices or other routine measures should also be strongly considered.
 
...
 
Whether or not patients have been discharged from the hospital, they will undergo the Study Day 2, Study Day 3, and Follow-up Day 30 visits to assess safety.
	Added details on precautions.	NS

3.6 Benefit and Risk Assessment	
Factor Xa inhibitors are a significant therapeutic advance in several indications. However, a significant risk of anticoagulation with FXa inhibitors is the potential for uncontrolled bleeding. While andexanet is approved for the management of acute major bleeding related to FXa inhibitor use, it is unknown whether it is efficacious and safe in patients who require urgent surgery in the setting of recent use of an FXa inhibitor. Andexanet may be beneficial in reversing anticoagulation and, thus, facilitating normal hemostasis during the surgical procedure.
	
Factor Xa inhibitors are a significant therapeutic advance in several indications. However, a significant risk of anticoagulation with FXa inhibitors is the potential for uncontrolled bleeding. In the case of urgent surgery, a delay in surgical treatment necessary to sufficiently diminish anti-coagulant concentrations could potentially result in deleterious clinical consequences. While andexanet is approved for the management of acute major bleeding related to FXa inhibitor use, it is unknown whether it is efficacious and safe in patients who require urgent surgery in the setting of recent use of an FXa inhibitor. Andexanet may be beneficial in reversing anticoagulation due to FXa inhibition and, thus, facilitating normal hemostasis during the surgical procedure.
 
...
 
Procedural risks inherent to the urgent surgical procedure itself would vary from based on the procedure type and individual patient risk factors, and should be additionally communicated to the patient by the treating physician.
	Added details to mitigate risks to patients.	NS
4.3 Criteria for Discontinuation from the Study	
The informed consent process will clearly alert patients to the negative effect that failure to complete the study has on its credibility.
 
...
 
Reasons for all study withdrawals will be recorded.
	
The informed consent process will clearly alert patients to the negative effect that failure to complete the study has on its credibility.
 
...
 
Reasons for all study withdrawals will be recorded in the eCRF.
	Removed text to clarify the informed consent process.	NS
4.4 Criteria for Discontinuation of Andexanet	
Patients who discontinue study drug may still continue in the study. Patients who discontinue from the study after receiving any amount of andexanet should undergo all follow-up safety procedures, in which case they should undergo an Early Termination
	
Patients who discontinue study drug may still continue in the study. Patients who discontinue from the study after receiving any amount of andexanet should undergo all follow-up safety procedures, in which case they should undergo an Early Termination
	Added text to clarify follow-up safety procedures for certain patients.	NS

	
visit. ...
 
Reasons for all discontinuations will be recorded.
	
visit- (complete the same procedures as Day 30 Visit).
 
...
 
Reasons for all discontinuations will be recorded in the eCRF.
		
5.0	
A summary of the patient visits and clinical evaluations can be found in Appendix A. Details on efficacy and safety assessments can be found in Section 10.0. Laboratory assessments or procedures performed per standard of care at presentation, but before signing of informed consent, may be used to assess eligibility.
	
A summary of the patient visits and clinical evaluations can be found in Appendix A. Details on efficacy and safety assessments can be found in Section 10.0. Laboratory assessments, clinical assessments, and/or procedures performed per investigator or institutional standard of care at presentation, but before signing of informed consent, may be used to assess eligibility fulfill protocol requirements.
	
Language changed to be inclusive of all assessments/ procedures and to provide clarity.
	NS
5.1 Screening Period 5.1.1 Subject Identification Numbers	
Patients will be considered to be in Screening once they have signed the ICF. At this time, patients will be assigned a patient identification number. Patients will be considered to have enrolled in the study once they have met the inclusion and exclusion criteria.
	
Patients will be considered to be in Screening once they have signed the ICF. At this time, patients will be assigned a patient identification number. Patients will be considered to have enrolled in the study once they have met the inclusion and exclusion criteria.
 
Patients will be identified by their need for urgent surgery that cannot be delayed and time from last dose of an FXa inhibitor. Informed consent will be administered followed by assignment of a patient identification number. Eligibility will be assessed by completion of demographics, medical history, physical examination, determination of last time of anticoagulated dose or plasma level. Baseline safety assessment will be performed inclusive of vital signs and weight, collection of local clinical laboratory results. Baseline efficacy and safety labs will be collected for analysis by a central laboratory. Following execution of the informed consent, changes
	
Language added to clarify how patients are identified and the assessments performed during Screening.
	NS

		in patient status that meet the definition of AEs will be recorded (Section 9.0).		
5.2 Visit Procedures (Days 1 to 30-37 , 2, 3, and 30)	The visit procedures are described in the Schedule of Activities (Appendix A).	
The visit procedures are described in the Schedule of Activities (Appendix A).
 
Day 1 Inpatient
 
On Day 1, patients will receive treatment with andexanet and will undergo the urgent surgery. Prior to start of dosing, patients will have the general health status assessed and categorized according to the American Society of Anesthesiologists Classification, repeat safety assessments (serial vital signs, repeat physical examination, and local labs). Study specific assessments and central laboratory samples will be collected to assess in vitro hemostasis.
 
The dose of andexanet will be selected based on anticoagulant product/brand, dose, and time of last dose of anticoagulant the patient is taking. The duration of the surgery will determine the total dose and duration of andexanet administered. Generally, it is planned for patients to complete the bolus and start infusion immediately prior to start of surgery and receive andexanet infusion, including extended dosing as necessary, for the duration of their surgical procedure. During the surgery, the investigator and staff will provide assessment of hemostasis and record all supporting medications related to hemostasis support. Patients should remain hospitalized on Day 1. The patient will be scheduled for study Day 2 visit.
 
Day 2 and Day 3
 
Follow-up visits on Days 2 and 3 will be conducted as an inpatient or outpatient. Patients will receive safety assessments (vital signs, physical examination, and local
	Details of procedures performed on specific days as well as rationale for dose selection have been added to the text to provide clarity.	S

		
laboratory testing) along with collection of samples for central laboratory analysis to assess hemostasis. Diagnostic and therapeutic products supporting hemostasis will be assessed, documented and reported. Adverse events and concomitant medications will be recorded. The patient will be scheduled for study Day 30 visit.
 
Day 30
 
The Follow-up visit on Day 30 will be conducted as an inpatient or outpatient. Safety assessments will be performed (vital signs, physical examination, weight, and local laboratory testing) along with collection of samples for central laboratory analysis to assess hemostasis. Adverse events and concomitant medications will be recorded. The investigator will assess and report duration of hospitalization by unit type (emergency, critical care units, post-op units, etc.) and document the survival status of the patient.
 
Procedures performed at the Day 30 visit will also be performed for all early terminating patients (Section 5.4).
		
5.3	
During the study, additional clinical visits may be scheduled at the Investigator's discretion in order to follow or evaluate AEs. The reason for an unscheduled visit will be recorded.
 
The following must be performed at an unscheduled visit:
 
 • Record the reason for the unscheduled visit. • Record AEs since last study visit. • Record use of concomitant medication since last study visit. 	
During the study, additional clinical visits may be scheduled at the Investigator's discretion in order to follow or evaluate AEs. care for the patient. The reason for an unscheduled visit will be recorded in the eCRF.
 
The following must be performed at an unscheduled visit:
 
 • Record the reason for the unscheduled visit. • Record AEs since last study visit. • Record use of concomitant medication since last study visit. 	
Wording changed for clarity and specified additional information to be captured at unscheduled visits.
	NS

	Additional procedures may be performed at an unscheduled visit as deemed necessary by the Investigator. These may include any of the central or local laboratory testing done at scheduled visits, vital signs, additional evaluations for bleeding, or assessment of AEs.	Additional procedures may be performed at an unscheduled visit as deemed necessary by the Investigator. These may include any of the central or local laboratory testing done at scheduled visits, vital signs, additional evaluations for bleeding, or assessment of AEs. Record study specified procedures and data captured as unscheduled visits.		
5.4	
An Early Termination visit will be conducted if the patient discontinues from the study before the Follow-up Day 30 visit. Procedures at this visit will include the following:
 
 • Record the reason for early termination. • Record AEs since last study visit. • Record use of concomitant medication since last study visit. • Record dates of use of anticoagulant(s) on the anticoagulant CRF. • Perform a final assessment of bleeding. • Collect central laboratory specimens for TG and antibodies (anti andexanet, anti-fX, anti fXa, anti-HCP, and nAbs). 
Vital signs and local laboratory assessments for complete blood count (CBC) and chemistry should also be performed at Early Termination only if these assessments have not yet been performed at any point during treatment.
	
An Early Termination visit will be conducted if the patient discontinues from the study before the Follow-up Day 30 visit. Procedures at this visit will include the following In addition to the Day 30 procedures outline in Section 5.2, the following procedures will be performed at the ET visit:
 
 • Record the reason for early termination. • Record AEs since last study visit. • Record use of concomitant medication since last study visit. • Record dates of use of anticoagulant(s) on the anticoagulant eCRF. • Perform a final assessment of bleeding. • Collect central laboratory specimens for TG and antibodies (anti andexanet, anti-fX, anti fXa, anti-HCP, and nAbs). 
Vital signs and local laboratory assessments for complete blood count (CBC) and chemistry should also be performed at Early Termination only if these assessments have not yet been performed at any point during treatment.
	
Clarified that the anticoagulant CRF is an electronic CRF.
 
Removed chemistry laboratory assessments from required assessments at Early Termination visit.
	NS
6.2 Dosing and Administration	The initial andexanet dosing regimen will consist of an IV bolus, immediately followed by an IV continuous infusion lasting for 2 hours, irrespective of the	The timing of andexanet dosing in relation to the surgical procedure is depicted schematically in Figure 3.	Revised text to more clearly and accurately explain	S

	
duration of surgery. The start of the bolus will occur prior to, but not more than 30 minutes before, the start of surgery (i.e., at the first incision). It is possible that the bolus or infusion may be ongoing at the start of surgery. There are 2 possible dosing regimens (Table 2).
 
If the initial andexanet dosing regimen (bolus plus continuous infusion; ~2.5 hours) is completed prior to the end of the procedure, the infusion should continue at a low dose (4 mg/min) through the end of the surgery and the immediate post-operative period. To facilitate the extended infusion, approximately 30 minutes prior to the end of the andexanet infusion, the investigator should inform the pharmacy whether additional andexanet will be needed, to allow time for preparation. The total length of the initial course of andexanet (initial bolus/infusion plus extended infusion) should last no longer than 6 hours.
 
If a post-operative patient meets the applicable criteria for andexanet re-dosing (Table 2), he/she may be re-dosed. All patients that are re-dosed will be administered a low-dose bolus (400 mg) plus continuous infusion (4 mg/min for 120 minutes). If a patient is re-dosed, a baseline anti-fXa activity sample will be drawn beforehand; no post-initiation anti-fXa activity will be obtained.
	
<Figure 3 inserted>
 
Key Dosing Directives:
 
 Initial Bolus (low/high-dose) must be completed prior to start of surgery (initial skin incision) Initial dosing (low/high-dose bolus + 120-min infusion) should be completely administered irrespective of surgery length. Infusion should continue throughout the duration of surgery, defined as skin incision to skin closure. Extended infusion (up to 4 hours at 4 mg/min) (1) may be administered to ensure continuous infusion to match the duration of the surgery, and (2) can additionally proceed into the immediate postoperative period per investigator discretion. 
Initial Dosing (Bolus + 2-hour infusion):
 
The initial andexanet dosing regimen will consist of the following:
 
 1. an IV bolus, (to be completed prior to surgery) 
followed immediately followed by
 
 2. an IV continuous infusion lasting for at least 2 hours, (irrespective of the duration of surgery). 
The start of the bolus will occur prior to, but should be initiated not more than 30 minutes before, and must be completed by, the start of surgery (i.e., at the first incision). The bolus will be followed immediately by a continuous infusion lasting at least 120 minutes, irrespective of the length of the surgery. It is possible that the bolus or infusion may be
	
andexanet dosing rules in relation to surgery timing and procedures.
	
--	--	--	---	--

	
ongoing at the start of surgery. There are 2 possible dosing regimens (Table 2).
 
If the end of surgery occurs prior to completion of the initial 2-hour infusion, the infusion should continue into the postoperative period until it is completed (120 minutes).
 
Extended Infusion (maximum of 4 additional hours at 4 mg/min)
 
Extended Infusion may be administered after completion of initial dose (bolus + 2-hour infusion):
 
1. To ensure continuous intraoperative infusion lasts the duration of the surgery, (if initial 2 hour infusion is completed prior to end of surgery) 
and
 
2. To provide coverage during the immediate postoperative period, per investigator clinical judgement 
If the initial andexanet dosing regimen (bolus plus continuous 2-hour infusion—2.5 hours) is completed prior to the end of the procedure, the infusion should continue at a low dose (only 4 mg/min) at least through the end of the surgery and (skin closure).
 
Extended infusion may also continue after the end of surgery per investigator clinical judgement if deemed appropriate for the immediate post-operative period.
 
To facilitate the extended infusion, approximately 30-45 minutes prior to the end of the andexanet infusion, the investigator should inform the pharmacy whether additional andexanet will be needed, to allow time for preparation. The total length of the initial course of andexanet (initial
	
--	---	--

